#### 5. PLANNED ANALYSES

The following analyses will be performed for this study:

- Regular and ad hoc review of aggregate safety data by DSMB
- Final Analysis of the Main Study

No formal interim analyses are planned.

## 5.1. DATA SAFETY MONITORING BOARD (DSMB)

A DSMB SAP, describing the methodology and presentation of results and access to results will be provided by the Sponsor as a separate document.

#### **5.2.** FINAL ANALYSIS

All final, planned analyses identified in this SAP will be performed following Sponsor Authorization of this SAP, Database Lock, Sponsor Authorization of Analysis Sets and Unblinding of Treatment. PK analysis will be performed and is described in this analysis plan.

After all subjects have completed the Main Study, outstanding data queries have been resolved/closed, and the data have been cleaned and finalized, the Sponsor will authorize breaking of the study blind and the final analysis of the data will be performed. The SAP must be approved and signed by the Sponsor before the database is locked and treatment assignment unblinded.

Any post-hoc, exploratory analyses completed to support planned study analyses, which were not identified in the SAP, will be documented and reported in the clinical study report. Any results from these unplanned analyses will also be clearly identified in the text of the clinical study report.

#### 6. ANALYSIS SETS

Agreement and authorization of subjects included/excluded from each analysis set will be conducted prior to the unblinding of the study. A summary of analysis sets will be presented.

### 6.1. SCREENED SET

The screened set will include all subjects who provide informed consent for this study.

#### **6.2.** ALL SUBJECTS ENROLLED SET

The enrolled set will include all subjects who are enrolled in the Run-in Period of this study.

## 6.3. FULL ANALYSIS SET [FAS]

The full analysis set (FAS) will include all randomized subjects, irrespective of whether they received study treatment. Subjects will be classified according to randomized treatment.

#### **6.4.** PER PROTOCOL SET

The Per Protocol set will include all subjects in the FAS without major protocol violations that might affect the evaluation of the effect of the study treatment on the primary endpoint. These protocol violations may include not meeting key inclusion/exclusion criteria, gross treatment non-compliance, receiving incorrect treatment, treatment unblinding by the investigator, or concomitant use of protocol-prohibited medications. The final determination on protocol violations, and thereby the composition of the Per Protocol set will be made prior to database lock of the Main Study and will be separately documented. Subjects will be summarized by treatment to which they were randomized, regardless of treatment actually received. If subjects are randomized but not treated, they will be excluded from Per Protocol set.

#### 6.5. SAFETY SET

The safety set will include all subjects who are randomized and receive at least one dose of study treatment. Subjects will be classified according to actual treatment received. If there is any doubt whether a subject was treated or not, they will be assumed treated by the randomized treatment for the purposes of analysis.

#### 6.6. PHARMACOKINETIC ANALYSIS SET

The pharmacokinetic analysis set will include all subjects in the FAS with at least 1 post-dose PK measurement who receive the active study drug, and who have at least 1 PK measurement at a scheduled post-dose or Ctrough PK timepoint after treatment started on Day 1 for at least 1 PK analyte , and who have no protocol violations or events with potential to affect the PK concentrations. Subjects will be classified according to the treatment received.

Only those in the PK analysis set who receive the active treatments will have PK (noncompartmental) or analyses (tabular or graphical summaries). In the case of a protocol violation/deviation or event that impacts PK, the affected PK sample data will be excluded from the summaries (i.e., the PK analysis set), but will still be reported in the study result listings. Protocol deviations impacting PK samples will be discussed in trial and adjudicated between IQVIA and Arena PK scientists and clinical pharmacologists, and the Protocol Deviation and its adjudication will be listed in listings.

#### 7. GENERAL CONSIDERATIONS

#### 7.1. REFERENCE START DATE AND STUDY DAY

Study Day will be calculated from the reference start date and will be used to show start/stop day of assessments and events. Reference start date is defined as Day 1, the date of randomization (Day 1 is the day of the first dose of study treatment) and will appear in every listing where an assessment date or event date appears.

- If the date of the event is on or after the reference date then:
  - Study day = (date of event reference date) + 1.
- If the date of the event is prior to the reference date then:
  - Study day = (date of event reference date).

In the situation where the event date is partial or missing, Study Day, and any corresponding durations will appear as missing in the listings. In the situation where the subject is randomized but not treated, the reference date is defined as the baseline visit date.

#### 7.2. BASELINE/POST-BASELINE

Unless otherwise specified, baseline is defined as the last non-missing measurement taken

#### Analysis Plan – Main Study

Page 17 of 77

prior to the reference start date. If measurements include time, the date/time will be used to define baseline; where time is not fully populated in the reference start date and fully populated in the measurement date, missing time values will be imputed to the earliest possible time measurement. Otherwise, only dates will be compared. In the case where the last non-missing measurement and the reference start date coincide and time is not collected, the measurement will be considered a baseline record, but adverse events (AEs) and medications commencing on the reference start date will be considered post-baseline records. For subjects randomized but not treated, baseline is defined as the last non-missing measurement taken on or before the baseline visit date.

Baseline AAPS is defined as the average abdominal pain score (APS) over the Run-in Period preceding the reference start date. The inclusion criteria to progress to randomization includes the requirement of "adequate compliance with entry of daily eDiary completed for ≥ 80% of days of the Run-in Period (Visit 2 to Visit 3 [Day 1])". Baseline AAPS will be calculated in the EDC system if at least 80% of the eDiary entries for APS are available and will be calculated as the average APS over all non-missing entries. If a subject has APS values recorded for less than 80% of the eDiary entries for the Run-in Period but is randomized, baseline AAPS will still be calculated based on the available APS.

Post-baseline AAPS at each week during the treatment period (Week 1 to Week 12) is calculated by taking the average value over each 7-day increment, beginning with the 7 days including and succeeding the Day 1 Visit, and continuing with 7-day increments for 12 weeks, regardless of the timing of the actual visits. AAPS during the follow-up period (Weeks 13 and 14) is calculated by taking the average value over the 7-day increment, beginning with the day after the last dose date, and continuing with 7-day increments for 2 weeks. If APS values are missing for more than 3 days in the 7-day window for the average weekly value, it will be reported as missing.

Post-baseline weekly AAPS by scheduled visit is calculated by taking the average value over the window of 7 days prior to and including the scheduled visit day if the endpoint is recorded for at least 4 of the 7 days in the window. If APS values are missing for more than 3 days in the 7-day window, the average value for the AAPS by scheduled visit will be reported as missing.

For other continuous endpoints collected in the Daily Diary form (e.g., bloating, discomfort, and number of bowel movements), baseline and post-baseline will be derived in the same manner.

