#### 7.7.4. Clinical Laboratory Assessments

All laboratory assessments required by the protocol will be performed by a central laboratory unless otherwise stated. The maximum amount of blood collected from each subject at a single visit will not exceed 85 mL. The maximum amount of blood collected from each subject over the duration of the Main Study, including any extra assessments that may be required will not exceed 350 mL. The maximum amount of blood collected from each subject over the duration of the LTE will not exceed 135 mL. Repeat or unscheduled samples may be taken for safety reasons or for technical issues with samples. Additional details regarding clinical laboratory sample collection, preparation, and shipment are provided in the Laboratory Manual.

Clinical safety laboratory tests should be completed pre-dose after the subject has fasted overnight (at least 8 hours). Clinical laboratory tests, including basic metabolic panel, and screening for drugs of abuse will be conducted at timepoints specified in the

The Investigator must review the laboratory report and document their review. Clinically significant worsening from baseline occurring during the study may be recorded as AEs at the Investigator's discretion. The laboratory reports must be filed with the source documents. Clinically significant abnormal laboratory findings are those that are not associated with the underlying disease, unless judged by the Investigator to be more severe than expected for the subject's condition.

All laboratory tests with values considered clinically significantly abnormal during participation in the study should be repeated until the values return to normal or baseline (Main Study Visit 3 or LTE Visit 2, as applicable) or are no longer considered clinically significant by the Investigator or Medical Monitor.

- If such values do not return to normal/baseline within a period of time judged reasonable by the Investigator, the etiology should be identified, and the Sponsor should be notified.
- All protocol-required laboratory assessments, as defined in the must be conducted in accordance with the Laboratory Manual.
- If laboratory values from non-protocol-specified laboratory assessments performed at the institution's local laboratory require a change in subject management or are considered clinically significant by the Investigator (eg, AE), then the results must be recorded in the eCRF.

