#### 19.3.1. LABORATORY REFERENCE RANGES AND MARKEDLY ABNORMAL CRITERIA

Quantitative laboratory measurements will be compared with the relevant laboratory reference ranges in SI units and categorized as:

- Low: Below the lower limit of the laboratory reference range.
- Normal: Within the laboratory reference range (upper and lower limit included).
- High: Above the upper limit of the laboratory reference range.
- Treatment-emergent high result: a change from a value less than or equal to the high limit at all baseline visits to a value greater than the high limit at any time during the treatment period.
- Treatment-emergent low result: a change from a value greater than or equal to the low limit at all baseline visits to a value less than the low limit at any time during the treament period.

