### 19.5. VITAL SIGNS

Orthostatic vital signs (VS) include the collection of blood pressure (BP) and HR after the subject has been resting in the supine position for at least 5 minutes and then again after 1 and 3 minutes of standing. For subjects enrolled before protocol amendment 2, there was an over-night observation period following randomization, and the orthostatic VS were collected at multiple timepoints on Day 1 and Day 2 (see below).

- Day 1: Prior to the first dose of study treatment and 2, 4, 8 hours after the first dose (prior to the second dose), and 10 hours after the first dose (2 hours after the second dose).
- Day 2: Prior to the first dose of study treatment and 2 and 4 hours after the first dose.

At all other visits after baseline, orthostatic vital signs were collected once per visit, prior to administration of the first daily dose of study treatment. For Day 1 and Day 2, the assessment at the earliest time of the same day will be used for analysis.

For subjects enrolled after protocol amendment 2, orthostatic BP and HR assessments were collected once per visit, prior to administration of the first daily dose of study treatment for the post-baseline visits.

The following VS data will be summarized using descriptive statistics by treatment group as well as for active treatment groups pooled.

- The actual measurement values of vital signs (BP and HR at Supine, Standing 1 and 3 minutes) at each visit/timepoint
- Change from baseline for orthostatic VS (BP and HR at Supine, Standing 1 and 3 minutes): calculated as post-baseline values minus the value prior to the first dose on Day 1.
- Change from supine to standing in orthostatic vital signs (BP and HR): calculated as the standing measurement minus the supine measurement by visit/timepoint. It will be calculated for 1-minute standing and 3-minute standing separately.

Body temperature and respiratory rate were collected once per visit, prior to the administration of the first daily dose of study treatment (for visits occurring during the Treatment Period). Change from baseline will be summarized in a similar manner. Baseline is defined as the last measurement collected before the first dose on Day 1.

Vital sign values meeting the criteria as defined in

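### Where the reference time is wholly missing, the SAP baseline rule rejects a timed pre-dose Day 1 lab or ECG and falls back to an earlier value

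*SAP*

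**What the plan says.** Main Study SAP 7.2 gives the general rule: "Unless otherwise specified, baseline is defined as the last non-missing measurement taken" before the reference start date. Section 7.1 fixes that reference: "Reference start date is defined as Day 1, the date of randomization". It adds that Day 1 is also the day of first dose, but it defines no time for the reference.

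For timed data, 7.2 says: "If measurements include time, the date/time will be used to define baseline". It then covers the case "where time is not fully populated in the reference start date and fully populated in the measurement date": there, "missing time values will be imputed to the earliest possible time measurement". A separate sentence keeps a same-day record as baseline, but only where no time was collected.

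LTE SAP 7.2 repeats the rule, with LTE randomization as the reference.

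Elsewhere the documents point to a Day 1 baseline:
- Protocol 7.7.4, on repeating abnormal lab tests, identifies "baseline (Main Study Visit 3 or LTE Visit 2, as applicable". It also asks for safety labs to be drawn before dosing.
- Main Study SAP 19.4 describes a pre-dose ECG on Day 1 and then refers to the other visits as coming after baseline.
- Main Study SAP 19.5, in its paragraph on temperature and respiratory rate, states: "Baseline is defined as the last measurement collected before the first dose on Day 1". For orthostatic blood pressure and heart rate it takes change from the value before the first dose on Day 1.

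The lab and ECG sections (19.3 and 19.4) contain no such statement, so 7.2 governs them.

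**The concern.** The imputation pushes the missing reference time to the start of the day, so a correctly timed pre-dose sample appears to come after it. The better-documented record is treated worse: an untimed Day 1 sample is kept as baseline and a timed one is rejected. Subjects randomized but never treated have their own clause in 7.2, which accepts values on or before the baseline visit date, so they keep Day 1. Treated subjects with timed records can lose it.

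Clinically relevant lab changes belong to the Main Study primary safety endpoint and to the LTE primary endpoint. These outputs depend on the baseline record:
- Main Study lab change and shift tables (19.3)
- Main Study ECG change and shift tables (19.4) and the counts of QTcF increases above 30 and 60 ms (19.4.1)
- LTE lab change and shift tables (LTE SAP 18.3)

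Main Study SAP 4.3 says that no definitions differ from the protocol, so a reader of the study report would not expect these tables to use anything but the Visit 3 value.

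**Working it through.** The documents give no figure to reproduce. The check applies the rule literally, taking baseline as the last record strictly before the reference date/time.

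**Assumed example:** a Screening record; a Day 1 pre-dose record at 08:30; first dose at 09:15; a 2-hour post-dose record at 11:15. The clock times are illustrative. The pre-dose and 2-hour timepoints are those in SAP 19.4 for ECGs after Amendment 2.

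| How the reference time is set | Reference used | Baseline selected |
|---|---|---|
| Actual first-dose time | 09:15 | Day 1 pre-dose |
| Wholly missing, earliest clock time | 00:00 | Screening |
| Wholly missing, earliest time measured that day | 08:30 | Screening |
| Hour known, minutes missing | 09:00 | Day 1 pre-dose |
| Wholly missing, latest clock time (not in the SAP) | 23:59 | Day 1, 2 h post-dose |

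1. With the reference at 00:00, none of the 24 × 60 = 1,440 clock minutes of Day 1 precedes it, so every timed Day 1 record fails.
2. The imputation wording could instead mean the earliest time actually measured. The result is the same, because 08:30 is not before 08:30.
3. If only the minutes are missing, the reference becomes 09:00 and the 08:30 record survives. Only a pre-dose record between 09:00 and 09:15 would be lost.
4. The same-day rule does not rescue the record, because it is limited to data collected without a time. Comparison by dates alone is the default only outside the timed-measurement case.
5. Replacing earliest with latest is not a repair, because it takes the post-dose ECG as baseline.

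**Age of a fallback value in the Main Study, if the last earlier value is from Screening.** Run-in lasts 14 to 19 days (protocol 3.5). Screening lasts up to 14 days, or 28 with biopsy (protocol 3.4).
- Minimum: about 14 days
- Maximum without biopsy: 14 + 19 = 33 days
- Maximum with biopsy: 28 + 19 = 47 days

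The range is conditional. Protocol 4.5 allows for lab and ECG results after Screening and before randomization, and the schedule of assessments is not in the public text. A more recent pre-Day 1 value would shorten the lag. The range does not apply to the LTE.

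**The case against.** The strongest defence is that this is an edge case with a purpose. The clause applies only when the reference time is incomplete, which suggests that the reference normally carries a time. Dosing has its own on-site form (SAP 16), and the PK analysis uses actual elapsed time from dosing (SAP 20.2), so dose times appear to be captured. Imputing the earliest time also keeps a 2-hour post-dose ECG from becoming baseline when the order is unknown. The intended baseline is visible in protocol 7.7.4 and SAP 19.4, and a programmer might follow that intent.

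Most of this limits the scope of the problem without removing it. The frequency is unknown, and partly missing times mostly survive. But section 7.1 does not link the reference to a recorded dose time, and the protection against post-dose values is bought by discarding valid pre-dose ones. Visible intent is not a stated override of 7.2.

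A reader might infer several stronger things that the documents do not support:
- **That every subject is affected.** This would require the reference to be stored as a date only. Section 7.1 is worded that way, but the dataset structure is not shown.
- **That pre-dose Day 1 abnormalities will be counted as treatment-emergent.** SAP 19.3.1 defines a treatment-emergent high as a change from a value not above the limit "at all baseline visits to a value greater than the high limit at any time during the treatment period". That wording refers to visits, and protocol 7.7.4 makes Visit 3 the lab baseline visit, so such a value may still count as baseline.
- **That baseline falls back to a Run-in value.** No Run-in lab or ECG can be confirmed from the public text.
- **That the arms are biased against each other.** The rule is the same for every arm, and no differential effect is shown.

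**Conclusion.** The rule is wrong as written for one defined case: the reference time is wholly missing and the Day 1 lab or ECG has a clock time. In that case the pre-dose Day 1 value cannot be baseline and an earlier value replaces it, contrary to the protocol's lab baseline visit. This holds under both readings of the imputation clause.

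It reaches Main Study labs and ECGs and LTE labs. Vital signs have their own baselines in both SAPs, as does AAPS, so the efficacy analysis of pain is untouched. LTE ECGs are summarized by value only (LTE SAP 18.4), so they have no change from baseline to distort.

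The number of subjects affected cannot be estimated. The Main Study lag of about 14 to 33 days, or up to 47 with biopsy, assumes that Screening supplies the last earlier value. Any effect on treatment-emergent lab flags depends on how SAP 19.3.1 is read. Severity is minor to moderate.

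**What to change.** In section 7.2 of both SAPs:
- Define baseline for labs and ECGs as the last non-missing value before the date/time of first dose (first LTE dose in the LTE).
- If the dose time is missing, accept Day 1 records at the nominal pre-dose timepoint and exclude nominal post-dose records.
- Delete the earliest-possible-time imputation, and do not substitute a latest-time one.

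The cost is a few lines of wording in two SAPs and one change to the baseline derivation. The pre-dose timepoints are already specified for safety labs (protocol 7.7.4) and for the Day 1 ECG (Main Study SAP 19.4), so no new data are needed.

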# 3. STUDY DESIGN

# 3.1. Overall Design

# 3.1.1. Main Study

The Main Study is designed to assess the efficacy, safety, and tolerability of olorinab in the treatment of abdominal pain in subjects with IBS with IBS-C or IBS-D who are not on concomitant treatment for IBS. This study is a Phase 2, multi-center, randomized, double-blind, placebo-controlled, parallel-group study that includes a Screening Period (up to 4 weeks for subjects who consent to colonic biopsy, up to 2 weeks for all other subjects), a Run-in Period (2 weeks), a randomized Main Study Treatment Period (12 weeks), and a post-treatment Main Study Follow-Up Period (2 weeks), totaling 16-20 weeks (Figure 1). After the Run-in Period, eligible subjects will be equally randomized into 1 of 4 treatment groups (olorinab 10, 25, or 50 mg tid or placebo tid). Randomization will be stratified by sex and IBS subtype. The number of subjects enrolled with IBS-C will be approximately equal to the number of subjects enrolled with IBS-D. An optional Long-Term Extension (LTE) is described in Section 3.1.2.

Figure 1: Schematic Diagram of Main Study Design

AAPS, average abdominal pain score; tid, 3 times per day; Wk, week

Notes: The Screening Period may be extended to up to a total of 4 weeks for subjects who consent to colonic biopsy. The last day of the Run-in Period is Day -1 and the first day of the Treatment Period is Day 1. There is not a designated Day 0 in this study. For Continuing subjects, Visit 9 of the Main Study may take place on the same day as Visit 2 of the Long-Term Extension.

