# 3.2. Scientific Rationale for Study Design

IBS is a GI disorder characterized by abdominal pain associated with defecation or change in bowel habits (Lacy 2016). Symptoms are chronic and may be episodic in nature, varying widely among patients (Miller 2014, Weinland 2011). In clinical studies of IBS, a run-in period of 1-3 weeks is recommended to monitor presence and consistency of symptoms according to study entry criteria (EMA 2014, FDA 2012, Miller 2014, Spiegel 2017). Accordingly, this study will incorporate a Main Study Run-in Period of at least 2 weeks (14-19 days), which will be used to

<sup>a Gap subjects start the LTE at Visit 1.

<sup>b Continuing subjects start the LTE at Visit 2.

train subjects on the proper completion of patient-reported outcome (PRO) instruments, to confirm subject eligibility with respect to abdominal pain severity, and to establish baseline values of various assessments.

Based on its mechanism of action as a selective CB2 agonist and data from previous nonclinical and clinical studies, it is anticipated that olorinab may have an effect on abdominal pain in patients with IBS, but will not have an effect on motility or bowel symptoms of constipation or diarrhea (Mathison 2004). Per FDA Guidance for Industry, Irritable bowel syndrome - clinical evaluation of drugs for treatment (FDA 2012), abdominal pain score (APS) is the recommended instrument for measuring pain in IBS. The instrument is a patient-reported outcome that uses an 11-point numeric rating scale ranging from 0 (no abdominal pain) to 10 (worst possible abdominal pain). The scale has been validated and has been widely used in clinical studies on pain in IBS (Spiegel 2009). Subjects in this study will record their worst abdominal pain over the previous 24 hours in a daily electronic diary (eDiary). Abdominal pain in IBS can fluctuate daily. To better capture a summary of subject pain, the AAPS (for Baseline: the average of all APS scores during the Run-In Period; for post-baseline visits: the average of the APS score over the 7 days before the scheduled visit) will be used to summarize subject pain and compare changes in pain over time. In the absence of significant safety findings, a greater decrease in AAPS in olorinab-treated subjects compared to placebo-treated subjects over the course of this study will provide supportive evidence that olorinab provides a direct benefit to subjects.

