#### 7. STUDY ASSESSMENTS AND PROCEDURES

#### 7.1. General Instructions

- Immediate safety concerns should be discussed with the sponsor immediately upon occurrence or awareness to determine if the subject should continue or discontinue study treatment.
- Adherence to the study design requirements, including those specified in the , is essential and required for study conduct.
- Study visits should be scheduled in the morning.
- The Investigator will maintain a screening/enrollment log to record details of all subjects screened and to confirm eligibility or record reasons for screening failure or Run-in failure, as applicable.

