## 7.5. Efficacy Assessments

[figure not shown]
All patient-reported efficacy data, including daily eDiary data will be captured electronically using hand-held devices. Daily eDiary entry will include: APS,

[figure not shown]
and treatment administration. Subjects will be instructed to complete daily eDiary entries in the evening, generally at the same time each day. eDiary entries will be completed at the times shown in the

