#### 17.1. DERIVATIONS

Compliance to study treatment is based on the Drug Accountability eCRF and will be calculated as the number of capsules/tablets taken (total dispensed – total returned) divided

by the prescribed number of capsules/tablets, expressed as a percentage (see calculations below).

The study treatment is given three times daily (tid), and it is assumed that the subject should take study treatment from the morning of the visit day at which their treatment is initially dispensed to the evening before their last treatment return date, as subjects are advised to wait to take their dose at the study site until all assessments and procedures have been completed on study days. For example, if the initial dispensation date is Day 1 and the last return date is Day 85, then the subject should have taken 3 capsules/tablets each day on Days 1 to 84; hence, the total number of prescribed capsules would be  $84 \times 3 = 252$ . Multiple bottles may be dispensed at one visit; in these cases, "Per Visit" compliance will be nonmissing if at least one bottle is returned.

• "Per Visit" Compliance to study treatment at Visit X will be calculated as follows:

```
\frac{([\text{N of Capsules dispensed at Visit }(X)] - [\text{N of Capsules returned at Visit }X+1])}{\{[\text{Date of Visit }X+1] - [\text{Date of Dispensing at Visit }(X)]\} \times 3} \times 100
```

• Overall Compliance to study treatment will be calculated as follows:

For subjects who permanently stop the study treatment before Week 12, the "Date of Visit X" in Overall Compliance calculations will be replaced by the date of study withdrawal.

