#### 7.2. BASELINE/POST-BASELINE

Unless otherwise specified, baseline is defined as the last non-missing measurement taken prior to the reference start date. If measurements include time, the date/time will be used to define baseline; where time is not fully populated in the reference start date and fully populated in the measurement date, missing time values will be imputed to the earliest possible time measurement. Otherwise, only dates will be compared. In the case where the last non-missing measurement and the reference start date coincide and time is not collected, the measurement will be considered a baseline record, but adverse events (AEs) and medications commencing on the reference start date will be considered post-baseline records. For subjects randomized but not treated, baseline is defined as the last non-missing measurement taken on or before the baseline visit date.

Main study baseline AAPS is defined as the average abdominal pain score (APS) over the main study Run-in Period preceding Visit 3. The detailed derivation can be found in the approved SAP for the Main Study.

LTE baseline AAPS is defined separately for continuing subjects and gap subjects. LTE baseline AAPS for continuing subjects is calculated using the Week 14 visit from the Main Study. Gap subject LTE baseline AAPS is calculated by taking the average value over the

window of 7 days prior to Day 1 in LTE.

Post-baseline weekly AAPS by scheduled visit is calculated by taking the average value over the window of 7 days prior to and including the scheduled visit day if the endpoint is recorded for at least 4 of the 7 days in the window. If APS values are missing for more than 3 days in the 7-day window, the average value for the AAPS by scheduled visit will be reported as missing.

For other continuous endpoints collected in the Daily Diary form (e.g., bloating, discomfort, and number of bowel movements), baseline and post-baseline will be derived in the same manner.

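### The SAPs' by-visit AAPS window takes in the visit-day evening diary entry, unlike the protocol's; Week 12 can then include an undosed day and the Continuing subjects' LTE baseline a post-dose entry

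*SAP*

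**What the plan says.** **Window.** Protocol 3.2 defines post-baseline AAPS as "the average of the APS score over the 7 days before the scheduled visit". Main Study SAP 7.2 defines by-visit AAPS as the "average value over the window of 7 days prior to and including the scheduled visit day", with a minimum of 4 daily scores, and LTE SAP 7.2 has the same rule. Main Study SAP 4.3 declares no departure from the protocol's analyses or definitions. LTE SAP 4.3 lists changes, but not this one.

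**Time of day.** Protocol 7.1: "Study visits should be scheduled in the morning". Protocol 7.5: "Subjects will be instructed to complete daily eDiary entries in the evening". Under 7.5.1 each entry scores the worst pain of the preceding 24 hours.

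**Dosing near Week 12.** Main Study SAP 17.1 counts expected doses from first dispensing "to the evening before their last treatment return date"; its example is Days 1 to 84 for a return on Day 85. Section 7.2 starts follow-up Week 13 on the day after the last dose.

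**LTE baseline.** The notes to Figure 1 in protocol 3.1.1 say that for Continuing subjects "Visit 9 of the Main Study may take place on the same day as Visit 2 of the Long-Term Extension". LTE SAP 7.1 makes LTE Day 1 the first-dose day. LTE SAP 7.2 says "LTE baseline AAPS for continuing subjects is calculated using the Week 14 visit from the Main Study"; for Gap subjects it uses the 7 days before LTE Day 1.

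**The concern.** A morning visit and an evening diary put the visit-day entry after the visit. Including that entry therefore brings post-visit time into the value labelled with the visit.

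At most visits this hardly matters, because dosing continues. At two visits treatment changes on or around the visit day:

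- **Week 12.** If dosing stops the evening before Visit 8, the last of the 7 days has no dose. Any effect lost that day pulls the olorinab-placebo difference toward zero. Main Study SAP 18.1.3 calls the by-visit change the supporting primary endpoint and allows a superiority statement from it. Protocol Table 6 names the by-visit model as the primary analysis. By-visit percent change in AAPS (18.2.3) uses the same value, and 7.2 derives other continuous diary endpoints the same way.
- **Week 14.** If Visit 9 is also LTE Visit 2, the evening entry follows the first LTE olorinab dose, including in subjects who came from placebo. A baseline should not contain treated time, and the Gap subjects' baseline does not.

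**Working it through.** **1. The plan's own power figure.** Inputs from protocol 8.1: difference 1.0, SD 1.9, 60 per arm, two-sided 0.05, two-sample t-test.

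Noncentrality = 1.0 / (1.9 × √(2/60)) = 1.0 / 0.3469 = 2.883, with 118 degrees of freedom. Power = 81.6%. The plan states at least 80%, so its figure is reproduced.

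**2. Undosed days in each Week 12 window.** Visit 8 is taken from Day 82 to Day 88 (Day 85 ± 3). The last dose is taken as the day before Visit 8, following SAP 17.1. Cells give undosed calendar days out of 7.

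| Visit 8 | SAP window, actual date | Protocol window | SAP window, nominal Day 85 (79–85) | By-week Week 12 (78–84) |
|---|---|---|---|---|
| Day 82 | 1 (76–82) | 0 (75–81) | 4 | 3 |
| Day 83 | 1 (77–83) | 0 (76–82) | 3 | 2 |
| Day 84 | 1 (78–84) | 0 (77–83) | 2 | 1 |
| Day 85 | 1 (79–85) | 0 (78–84) | 1 | 0 |
| Day 86 | 1 (80–86) | 0 (79–85) | 0 | 0 |
| Day 87 | 1 (81–87) | 0 (80–86) | 0 | 0 |
| Day 88 | 1 (82–88) | 0 (81–87) | 0 | 0 |

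Follow-up Week 13 starts the day after the last dose. On this schedule that is the Visit 8 day itself, so the same entry counts as by-visit Week 12 and as by-week follow-up Week 13.

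**3. Illustrative dilution.** Let r be the share of the effect kept on the undosed day, with all 7 entries present and the SD unchanged. The documents give no value for r, so it is an assumption shown over its range. Difference = (6 + r)/7 × 1.0.

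| r | Difference | Noncentrality | Power per dose |
|---|---|---|---|
| 1 | 1.000 | 2.883 | 81.6% |
| 0.5 | 6.5/7 = 0.929 | 2.677 | 75.6% |
| 0 | 6/7 = 0.857 | 2.471 | 68.8% |

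**4. LTE baseline on a same-day start.** The by-visit Week 14 window ends on the Visit 9 day, which is also LTE Day 1, so 1 of its 7 days carries an entry made after the first LTE dose. Under the Gap rule the count is 0 of 7.

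**The case against.** **The Week 12 visit day may not be undosed.** SAP 17.1 is a drug-accountability assumption, not a dosing instruction. Section 20.2 treats the Week 12 trough sample as pre-dose and limits trough summaries to samples taken within an hour before a dose that day. Section 16 takes the last-dose date from an on-site dosing form. Against that, the sampling text in SAP 4.1 lists Weeks 2 to 10 as sampled before the first daily dose and puts Week 12 with Week 14, an off-treatment visit. The documents do not settle this.

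**The anchor is not stated.** The actual visit date is the likelier reading, because only the by-week rule is said to ignore actual visit timing. But 7.4 also refers to protocol-scheduled days, and the window table is not visible. With a nominal Day 85 anchor the count runs from 4 to 0; with a nominal Day 84 anchor the window is simply Days 78–84.

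A reader might therefore infer an off-drug day for every completer. That is too strong. It also needs a visit-day entry to exist. And because the 24-hour recall reaches back to about the last evening dose, an undosed calendar day is not a fully drug-free recall period.

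**The primary analysis is not affected.** A reader might attach the power loss to the study's main result. The SAP's primary analysis is by week from Day 1 and does not use this window, nor do the four tests that define success.

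**The LTE consequence is small.** LTE efficacy is descriptive, with no between-treatment tests, change from Main Study baseline is also defined, and the study was ended early. The LTE SAP does not say which Week 14 value it means, and the by-week one (Days 92–98 after a Day 84 last dose) would miss a Day 99 visit. That reading is not a full escape: if Visit 9 and the first LTE dose fall on Day 95, Days 95–98, or 4 of 7, are post-dose.

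What stands after all this is the undeclared conflict between protocol 3.2 and SAP 7.2, and the post-visit timing of the added entry. Neither depends on any dosing assumption.

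**Conclusion.** The by-visit window in both SAPs departs from the protocol without saying so, and the extra entry is made after the visit.

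At Week 12 this gives one undosed calendar day in 7 (14%) for each completer with a visit-day entry, on two conditions: dosing follows SAP 17.1, and the window is tied to the actual visit date. Any loss of effect on that day biases the by-visit difference toward zero. The falls in power to 75.6% and 68.8% are illustrative, not forecasts. They apply to the supporting by-visit analysis only, since the documents give no rate at which the effect wears off.

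In the LTE, a same-day Visit 9 and LTE Visit 2 can put one post-dose entry in 7 into the Continuing baseline if the by-visit value is used. The inconsistency with the Gap rule is real, but the effect on conclusions is small.

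A reader might also hope that realigning the windows cures an old baseline in Continuing subjects who start the LTE late. It does not. Counting from the Week 12 visit, LTE Visit 2 can be 27 days later and Visit 9 as early as 11, a gap of 16 days, and the fallback below uses the same older diary days.

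This should be corrected, but it does not threaten the SAP's primary result.

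**What to change.** - In section 7.2 of both SAPs, define by-visit AAPS as the 7 days before the actual visit date (visit day −7 to −1), with at least 4 entries.
- Define LTE baseline AAPS for all subjects from the 7 diary days before LTE Day 1, excluding Day 1. For Continuing subjects with no diary in that window, use the last 7 Main Study follow-up diary days before LTE Day 1.
- Reconcile Main Study SAP 16, 17.1 and 20.2 on whether a dose is taken on the Week 12 visit day.
- If the inclusive window is preferred, declare and justify it in section 4.3 of each SAP.

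The cost is SAP wording and a one-day shift in the derivation, with no new data. Under SAP 17.1 dosing, undosed days in by-visit Week 12 and post-dose days in same-day LTE baselines both go from 1 of 7 to 0.

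There are two limits. For a Visit 8 on Day 85, the by-visit window then coincides with by-week Week 12 (Days 78–84), so the supporting analysis adds less. And the change does not remove the 3, 2 or 1 undosed days in by-week Week 12 when Visit 8 falls on Day 82, 83 or 84.
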